### **5.6.3 Use in Pregnancy**

If a subject inadvertently becomes pregnant while on treatment with pembrolizumab and XL888, the subject will immediately be removed from the study. The site will contact the subject at least monthly and document the subject's status until the pregnancy has been completed or terminated. The outcome of the pregnancy will be reported to the Sponsor and to Merck and Exelixis without delay and within 24 hours to the Sponsor and within 2 working days to Merck and Exelixis if the outcome is a serious adverse experience (e.g., death, abortion, congenital anomaly, or other disabling or life-threatening complication to the mother or newborn).

The study investigator will make every effort to obtain permission to follow the outcome of the pregnancy and report the condition of the fetus or newborn to the Sponsor. If a male subject impregnates his female partner the study personnel at the site must be informed immediately and the pregnancy reported to Merck and Exelixis as described above and in Section 7.2.2.

### **5.6.4 Use in Nursing Women**

It is unknown whether pembrolizumab is excreted in human milk. Since many drugs are excreted in human milk, and because of the potential for serious adverse reactions in the nursing infant, subjects who are breast-feeding are not eligible for enrollment. Patients should be advised not to breastfeed while on XL888 or for at least 3 months after discontinuation.

## **5.7 Subject Withdrawal/Discontinuation Criteria**

Subjects may withdraw consent at any time for any reason or be dropped from the trial at the discretion of the investigator should any untoward effect occur. In addition, a subject may be withdrawn by the investigator or the Sponsor if enrollment into the trial is inappropriate, the trial plan is violated, or for administrative and/or other safety reasons. Specific details regarding discontinuation or withdrawal are provided in Section 7.1.4 – Other Procedures.

A subject must be discontinued from the trial for any of the following reasons:

- The subject or legal representative (such as a parent or legal guardian) withdraws consent.
- Confirmed radiographic disease progression

*Note:* For unconfirmed radiographic disease progression, please see Section 5.2.2

*Note: A subject may be granted an exception to continue on treatment with confirmed radiographic progression if clinically stable or clinically improved, please see Section 7.1.2.7.1*

- Unacceptable adverse experiences as described in Section 5.2.1.2
- Intercurrent illness that prevents further administration of treatment
- Investigator's decision to withdraw the subject
- The subject has a confirmed positive serum pregnancy test
- Noncompliance with trial treatment or procedure requirements
- The subject is lost to follow-up
- Completed 24 months of uninterrupted treatment with pembrolizumab or 35 administrations of study medication, whichever is later.

*Note: 24 months of study medication is calculated from the date of first dose. Subjects who stop pembrolizumab/XL888 after 24 months may be eligible for up to one year of additional study treatment if they progress after stopping study treatment provided they meet the requirements detailed in Section 7.1.5.5*

- Administrative reasons

The End of Treatment and Follow-up visit procedures are listed in Section 6 (Protocol Flow Chart) and Section 7.1.5 (Visit Requirements). After the end of treatment, each subject will be followed for 30 days for adverse event monitoring (serious adverse events will be collected for 90 days after the end of treatment as described in Section 7.2.3.1). Subjects who discontinue for reasons other than progressive disease will have post-treatment follow-up for disease status until disease progression, initiating a non-study cancer treatment, withdrawing consent or becoming lost to follow-up. After documented disease progression each subject will be followed by telephone for overall survival until death, withdrawal of consent, or the end of the study, whichever occurs first.

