#### **5.3.1 Pembrolizumab**

Adverse events (both non-serious and serious) associated with pembrolizumab exposure may represent an immunologic etiology. These adverse events may occur shortly after the first dose or several months after the last dose of treatment. Pembrolizumab must be withheld for drug-related toxicities and severe or life-threatening AEs as per 3 below. See Section 5.6 for supportive care guidelines, including use of corticosteroids.

Toxicities unrelated to pembrolizumab will not ordinarily result in the modification of pembrolizumab dose. AEs will be defined based on the National Cancer Institute (NCI) Common Terminology Criteria for Adverse Events (CTCAE) version 4.

Table 3 Dose Modification Guidelines for Drug-Related Adverse Events

General instructions:				

 
1. Corticosteroid taper should be initiated upon AE improving to Grade 1 or less and continue to taper over at least 4 weeks.
 
2. For situations where pembrolizumab has been withheld, pembrolizumab can be resumed after AE has been reduced to Grade 1 or 0 and corticosteroid has been tapered. Pembrolizumab should be permanently discontinued if AE does not resolve within 12 weeks of last dose or corticosteroids cannot be reduced to <math>\leq 10</math> mg prednisone or equivalent per day within 12 weeks.
 
3. For severe and life-threatening irAEs, IV corticosteroid should be initiated first followed by oral steroid. Other immunosuppressive treatment should be initiated if irAEs cannot be controlled by corticosteroids.
 
				
Immune-related AEs	Toxicity grade or conditions (CTCAEv4.0)	Action taken to pembrolizumab	irAE management with corticosteroid and/or other therapies	Monitor and follow-up
Pneumonitis	Grade 2	Withhold	
 
• Administer corticosteroids (initial dose of 1-2 mg/kg prednisone or equivalent) followed by taper
 
	
 
• Monitor participants for signs and symptoms of pneumonitis
 
• Evaluate participants with suspected pneumonitis with radiographic imaging and initiate corticosteroid treatment
 
• Add prophylactic antibiotics for opportunistic infections
 

	Grade 3 or 4, or recurrent Grade 2	Permanently discontinue		

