### **5.7.2 Subject Replacement Strategy**

Patients who do not complete the intended course of chemotherapy due to reasons other than toxicity will be considered as in-evaluable for the primary endpoint and will be replaced.

[illegible]

Trial Period:	Treatment Cycles a									End of Treatment	Post-Treatment		
Treatment Cycle/Title:	Main Study Screening (Visit 2)	1	2	3	4	5	To be repeated beyond 8 cycles			Discon	Safety Follow-up	Follow Up Visits b	Survival Follow-Up
Scheduling Window (Days):	-28 to -1	± 3	± 3	± 3	± 3	± 3	± 3	± 3	± 3	At time of Discon	30 days post discon ± 7 days	Every 8 weeks post discon	Every 12 weeks
Comprehensive Serum Chemistry Panel	X	X	X	X	X	X	X	X	X	X	X	X	
Fasting triglyceride, cholesterol and glucose	X			X				X					
Urinalysis	X			X				X		X			
T3, FT4 and TSH	X		X			X			X	X	X		
ECG g	X	X	X		X		X g		X g				
Tumor Imaging	X f			X h			X h						
Archival or Newly Obtained Tissue Collection i	X	X											
Correlative Studies Blood Collection j	X	X	X	X						X			

- Treatment cycles are 3 weeks
- Only for patients with ongoing treatment related toxicities
- Pembrolizumab will be given day 1, XL888 twice weekly orally
- ECOG performance status should be done within 10 days or less from day 1 of cycle 1
- Ophthalmologic exam done at baseline and repeated only if there are symptoms
- Baseline imaging with 8 weeks of day 1 is acceptable
- ECG day1 2 to 3 hours after administration of XL888 every other cycle after C2 (C1, C2, C4, C6 etc)
- Scans will be done every 3 cycles between day 15 and day 21
- Paired biopsies will only be obtained from 16 patients on the dose expansion cohort
- Samples will be collected at baseline, day 15, and every cycle for the first 9 weeks. Analysis will include proportion of T, B, NK, memory and effector T cell subsets and expression of PD-1, PD-L1 and B7 family members. Samples will be collected at baseline and on weeks 6 and 9. This will be performed using interferon- gamma and CD107.

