#### **7.1.5 Safety Follow-Up Visit**

The mandatory Safety Follow-Up Visit should be conducted approximately 30 days after the last dose of trial treatment or before the initiation of a new anti-cancer treatment, whichever comes first. All AEs that occur prior to the Safety Follow-Up Visit should be recorded. Subjects with an AE of Grade > 1 will be followed until the resolution of the AE to Grade 0-1 or until the beginning of a new anti-neoplastic therapy, whichever occurs first. SAEs that occur within 90 days of the end of treatment or before initiation of a new anti-cancer treatment should also be followed and recorded. Subjects who are eligible for retreatment with pembrolizumab/XL888 (as described in Section 7.1.6.2) may have up to two safety follow-up visits, one after the Treatment Period and one after the Second Course Phase.

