#### **7.1.6.1 Survival Follow-up**

Once a subject experiences confirmed disease progression or starts a new anti-cancer therapy, the subject moves into the survival follow-up phase and should be contacted by telephone every 12 weeks to assess for survival status until death, withdrawal of consent, or the end of the study, whichever occurs first.

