### 7.2.3 Serious Adverse Events

A serious adverse event is any adverse event occurring at any dose or during any use of investigational product that:

- Results in death;
- Is life threatening;
- Results in persistent or significant disability/incapacity;
- Results in or prolongs an existing inpatient hospitalization;
- Is a congenital anomaly/birth defect;
- Is another important medical event
- **Note:** In addition to the above criteria, adverse events meeting either of the below criteria, although not serious per ICH definition, are reportable to the Merck and Exelixis in the same timeframe as SAEs to meet certain local requirements. Therefore, these events are considered serious by Merck/ Exelixis for collection purposes.
  - Is a new cancer (that is not a condition of the study);

- Is associated with an overdose.

Refer to Table 6 for additional details regarding each of the above criteria.

For the time period beginning when the consent form is signed until treatment allocation/randomization, any serious adverse event, or follow up to a serious adverse event, including death due to any cause that occurs to any subject must be reported within 24 hours to Sponsor and within 2 working days to Merck Global Safety and Exelixis if it causes the subject to be excluded from the trial, or is the result of a protocol-specified intervention, including but not limited to washout or discontinuation of usual therapy, diet, placebo treatment or a procedure.

For the time period beginning at treatment allocation/randomization through 90 days following cessation of treatment, or 30 days following cessation of treatment if the subject initiates new anticancer therapy, whichever is earlier, any serious adverse event, or follow up to a serious adverse event, including death due to any cause whether or not related to the Exelixis and Merck product, must be reported within 24 hours to sponsor and within 2 working days to Exelixis and Merck Global Safety.

Serious adverse events related to study treatment or study procedures must be recorded even if the SAE occurs more than 30 days after cessation of treatment and also must be reported immediately to the Sponsor and to Exelixis and Merck Global Safety.

All subjects with serious adverse events must be followed up for outcome.

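### SAEs are to be collected to day 90, but for patients who stop for progression with no ongoing toxicity and no new therapy, the readable text schedules no safety enquiry after the day 30 visit

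*Combined protocol and SAP*

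**What the plan says.** **The window.** Section 5.7 states that "each subject will be followed for 30 days for adverse event monitoring", while "serious adverse events will be collected for 90 days after the end of treatment". Section 7.2.3 makes SAEs reportable to day 90 whether or not related, but shortens the period: "or 30 days following cessation of treatment if the subject initiates new anticancer therapy, whichever is earlier". Section 7.2.4.1 gives events of clinical interest the same two limits.

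**The contacts after treatment.**
- Section 7.1.5: "The mandatory Safety Follow-Up Visit should be conducted approximately 30 days after the last dose of trial treatment". It comes earlier if new anticancer treatment starts first. The flow chart (Section 6.1) times it at "30 days post discon ± 7 days".
- The flow chart also has follow-up visits every 8 weeks, with a footnote restricting them: "Only for patients with ongoing treatment related toxicities".
- Section 7.1.6 gives patients who stop for a reason other than progression imaging every 6 weeks to monitor disease status.
- Section 7.1.6.1 says that a patient with confirmed progression, or on new therapy, "should be contacted by telephone every 12 weeks to assess for survival status until death". Section 5.7 likewise describes telephone follow-up after progression as being for overall survival.

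**Late events.** On adverse events associated with pembrolizumab, Section 5.3.1 says: "These adverse events may occur shortly after the first dose or several months after the last dose of treatment".

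**The concern.** The collection period and the contact schedule do not match. The plan asks for SAEs over 90 days, but the last contact at which every patient is asked about safety comes about a third of the way through. For a patient who then moves to survival follow-up, the only described contact has a different purpose. If that patient is admitted elsewhere on day 60, the site has a duty to report but no planned occasion on which to learn of the admission.

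The toxicity profile is a secondary objective (Section 3.2), and confirming safety and tolerability is the stated aim of the expansion phase (Section 8.1). The unqueried period is also one in which Section 5.3.1 expects immune events to be possible. With 32 expansion patients, one or two unseen late SAEs would visibly change the reported percentage.

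**Working it through.** The plan gives no event count or rate for this period, so there is no figure to reproduce. The check is a comparison of the schedule with the window, followed by an illustration.

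**Inputs**
- SAE window: 90 days (5.7, 7.1.5, 7.2.3).
- Safety Follow-Up Visit: 30 ± 7, that is day 23 to day 37 (6.1, 7.1.5).
- Toxicity follow-up visit: 8 × 7 = day 56 (6.1).
- Survival call: 12 × 7 = 84 days after a start that the documents do not give (6.1, 7.1.6.1).
- Expansion patients: 32 (8.1).

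Day 0 is taken as the end of treatment, and last dose and discontinuation are treated as the same day.

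**Step 1: who has a contact between the day 30 visit and day 90**

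| Patient | Contact in the readable text | Gap? |
|---|---|---|
| Ongoing treatment-related toxicity, any reason for stopping | Visit near day 56 (6.1) | No |
| AE above Grade 1 at the safety visit | Followed to Grade 0-1 or new therapy (7.1.5) | No, while followed |
| New therapy started by day 30 | SAE window closes at day 30 (7.2.3) | No |
| Stopped without progression | Imaging at 42 ± 7 and 84 ± 7 days, if counted from the end of treatment (7.1.6) | Contact exists, but no SAE question is described |
| Stopped for progression, none of the above | Survival call only (5.7, 7.1.6.1) | Yes |

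**Step 2: length of the gap in the last row**

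Days without a scheduled safety enquiry = 90 − day of safety visit.
- Visit on day 37: 90 − 37 = 53 days; 53/90 = 59%.
- Visit on day 30: 90 − 30 = 60 days; 60/90 = 67%.
- Visit on day 23: 90 − 23 = 67 days; 67/90 = 74%.

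**Step 3: could the survival call close the gap?**

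If the 12 weeks run from the end of treatment, the call is on day 84. Even with a safety question added, the last 90 − 84 = 6 days would be uncovered. If the clock starts d days after the end of treatment, the call is on day 84 + d, inside the window only if d ≤ 6. For d = 7, 21 and 30 it falls on days 91, 105 and 114.

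**Step 4: illustration under assumed rates**

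Patients with a late SAE that depends on unsolicited reporting = 32 × q × f, where q is the proportion with an SAE in days 31 to 90 and f is the share of patients in the gap. Neither is in the documents; I assume 5% to 20% and 25% to 75%.
- Low: 32 × 0.05 × 0.25 = 0.4.
- Middle: 32 × 0.10 × 0.50 = 1.6.
- High: 32 × 0.20 × 0.75 = 4.8.

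If 20% to 50% of these were never reported, about 0.1 (0.4 × 0.20) to 2.4 (4.8 × 0.50) would be missed.

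**The case against.** The strongest reply has four parts.

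- **The schedule is only partly readable.** The upper rows of the flow chart are illegible in this copy, and an adverse-event row could sit there. Section 7.1.2.1 sends the reader to that chart and says that adverse experiences are recorded during follow-up as well. This stands as a limit: the absence of a safety question rests on how Sections 5.7 and 7.1.6.1 describe the call. Section 7.1.2.1 itself sets no contact date.
- **Reporting is mandatory.** Section 7.2.3 requires all SAEs in the window to be reported and related ones to be recorded after day 30. Section 10.5 has the team review the logs. A reader might infer from the gap that late SAEs are under-counted. The documents show only a risk of that. But the duty operates only once the site knows of the event, and no contact is attached to it.
- **Many patients are outside the gap.** A reader might infer that everyone who progresses goes without safety contact. That is wrong for patients with ongoing toxicity, and the shorter window for new therapy removes others. For the same reason, an SAE rate should not be applied to all 32 expansion patients. Nor do the documents show that those in the gap are the largest group.
- **The comparison between groups is weak.** It is tempting to say that SAEs are actively sought in patients who stop without progression and not in those who progress, so that the rate is biased by reason for stopping. Section 7.1.6 gives the former imaging for disease status, with no SAE question described. They have more contacts, but the text does not support a claim of active ascertainment.

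The recommended dose is not affected, since DLTs are judged in the first weeks of therapy, and Section 8.3 makes the analyses descriptive. What remains is the patient who was well at the day 30 visit and has a new event later. Follow-up of existing toxicity does not reach that patient.

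**Conclusion.** The point holds for a defined subgroup: patients who stop for progression, have no ongoing toxicity and have not started new anticancer therapy. For them the readable text schedules no safety enquiry for 53 to 67 of the 90 days in which SAEs are to be collected, and new-onset SAEs may be under-ascertained. The day counts follow from the plan's own figures. The number of patients does not: 0.4 to 4.8 of 32 is an illustration resting on assumed event rates and an assumed share in the gap.

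A survival call on day 84 should not be taken as given, because the start of the 12-week clock is undefined. The conclusion also assumes that the illegible chart rows contain no adverse-event check at the survival call. This is a modest weakness in safety data collection, worth correcting because correction is cheap.

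**What to change.** In Sections 6.1, 7.1.5 and 7.1.6.1, schedule one contact at day 90 (+7) after the end of treatment for each patient whose 90-day SAE window is still open. For patients who progressed, this is the first survival call. For others, it is a call or the nearest follow-up contact. At that contact:
- ask, and record yes or no, about hospital admissions, SAEs and immune-related events since the Safety Follow-Up Visit;
- record the start date of any new anticancer therapy, so that the shorter window in Section 7.2.3 can be applied.

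Later survival calls stay every 12 weeks. Fixing the first call to the end of treatment also settles the undefined clock for these patients.

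Two related places should be reconciled in the same edit. Section 5.7 refers to a Section 7.2.3.1 that does not appear; the window is in 7.2.3. The 6-weekly follow-up in Section 7.1.6 also needs to be squared with the 8-weekly visits, limited to ongoing toxicity, in the flow chart.

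The cost is a short scripted question and no added clinic visit for patients who progressed; some others may need one extra call. Reported SAE rates may rise slightly.

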### **5.7.1 Discontinuation of Study Therapy after CR**

Discontinuation of treatment may be considered for subjects who have attained a confirmed CR that have been treated for at least 24 weeks with pembrolizumab and XL888 and had at least two treatments with pembrolizumab and XL888 beyond the date when the initial CR was declared. Subjects who then experience radiographic disease progression may be eligible for additional treatment with pembrolizumab and XL888 via the Second Course Phase at the discretion of the investigator as detailed in Section 7.1.6.2.

### **5.7.2 Subject Replacement Strategy**

Patients who do not complete the intended course of chemotherapy due to reasons other than toxicity will be considered as in-evaluable for the primary endpoint and will be replaced.

[illegible]

Trial Period:	Treatment Cycles a									End of Treatment	Post-Treatment		
Treatment Cycle/Title:	Main Study Screening (Visit 2)	1	2	3	4	5	To be repeated beyond 8 cycles			Discon	Safety Follow-up	Follow Up Visits b	Survival Follow-Up
Scheduling Window (Days):	-28 to -1	± 3	± 3	± 3	± 3	± 3	± 3	± 3	± 3	At time of Discon	30 days post discon ± 7 days	Every 8 weeks post discon	Every 12 weeks
Comprehensive Serum Chemistry Panel	X	X	X	X	X	X	X	X	X	X	X	X	
Fasting triglyceride, cholesterol and glucose	X			X				X					
Urinalysis	X			X				X		X			
T3, FT4 and TSH	X		X			X			X	X	X		
ECG g	X	X	X		X		X g		X g				
Tumor Imaging	X f			X h			X h						
Archival or Newly Obtained Tissue Collection i	X	X											
Correlative Studies Blood Collection j	X	X	X	X						X			

- Treatment cycles are 3 weeks
- Only for patients with ongoing treatment related toxicities
- Pembrolizumab will be given day 1, XL888 twice weekly orally
- ECOG performance status should be done within 10 days or less from day 1 of cycle 1
- Ophthalmologic exam done at baseline and repeated only if there are symptoms
- Baseline imaging with 8 weeks of day 1 is acceptable
- ECG day1 2 to 3 hours after administration of XL888 every other cycle after C2 (C1, C2, C4, C6 etc)
- Scans will be done every 3 cycles between day 15 and day 21
- Paired biopsies will only be obtained from 16 patients on the dose expansion cohort
- Samples will be collected at baseline, day 15, and every cycle for the first 9 weeks. Analysis will include proportion of T, B, NK, memory and effector T cell subsets and expression of PD-1, PD-L1 and B7 family members. Samples will be collected at baseline and on weeks 6 and 9. This will be performed using interferon- gamma and CD107.

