## 2.0 TRIAL DESIGN

Open label phase I trial. Primary objective is to determine the recommended phase 2 dose (RP2D) of the combination of XL888 and pembrolizumab. The design is 3+3 with 3 dose levels of XL888 (X). MTD is defined as the dose at which less than one-third of the subjects experience a DLT in the first 4 weeks of treatment.

After determining the RP2D, an additional 16 patients with pancreatic cancer (Arm A) and 16 patients with colorectal cancer (Arm B) will be enrolled in an expansion phase to confirm toxicity profile and obtain paired biopsies. Paired biopsy performed on 8 patients in each group. Patient selected for biopsy must have a primary or metastatic non-bone site that is amenable to safe biopsy. Bone only lesions are not suitable for biopsy. Patients undergoing paired biopsies will be assigned into two treatment cohorts (8 in each) and treated according to the schema below.

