#### **4.2.1 Rationale for Endpoints**

- 4.2.1.1 Efficacy Endpoints:** This is a phase I trial. The primary endpoint is still toxicity. The plan is to evaluate the response rate, response duration, and progression free

survival of the patients on the trial. These endpoints will provide preliminary data in two patient subsets: patients with pancreatobiliary and other GI malignancies.

- 4.2.1.2 **Biomarker Research:** We intend in all patients to evaluate the effects of the combination on T-cell population in peripheral blood. In addition, we plan to evaluate the effects of the combination versus pembrolizumab alone in paired biopsy samples in 16 patients. These samples will be analyzed for tumor infiltrating lymphocytes, stromal/tumor markers and expression immune inhibitory molecules (PD-L1, PD-L2, PD1, etc). We anticipate to see a difference between the group treated with the combination versus the group treated with pembrolizumab alone.

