**Dose level 3 will only be tested if we observe 2 DLT's on dose level 2.**

### 5.2.2 Dose Escalation

Starting dose of 45mg; if  $\geq 2$  patients with DLTs in 3 ( $\geq 2/3$ ) or 6 ( $\geq 2/6$ ) subjects; stop and consider reduced dose of XL888. If not, increase dose to 90 mg and test 3-6 patients. If  $\geq 2$  patients with DLTs in 3 or 6 subjects, reduce dose to 60 mg and try again. If an acceptable dose is identified, treat 16 more patients at the MTD. Prior to dose escalation, we will obtain approval from the Data Safety and Monitoring Committee (DSMC).

**5.2.3 Dose limiting toxicity (DLT)** will be defined as any of the following definitely treatment related adverse events during the first 21 days of therapy:

- Grade IV neutropenia lasting more than 8 days; any neutropenic fever or sepsis;
- Grade III with clinically significant bleeding or any grade IV thrombocytopenia;
- Grade III nausea, vomiting, or diarrhea, lasting  $>72$  hours despite adequate supportive care;
- Other non-hematologic treatment-related toxicity at Grade III or higher
- Grade 4 asymptomatic laboratory abnormalities that last for more than 24 hours or Grade 3 asymptomatic laboratory abnormalities lasting more than 21 days is a DLT.
- Grade IV or higher diarrhea, nausea, vomiting
- In ability to take more than 75% of XL888 due to toxicity.

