#### **7.1.1.6 Trial Compliance (Medication/Diet/Activity/Other)**

Compliance with XL888 will be determined using drug diary and pill counts performed on day 1 of each cycle. Patients who take less than 80% of their prescribed dose of pembrolizumab and/or XL888 due to reasons other than toxicity will be considered inevaluable for the primary endpoint of toxicity and will be replaced.

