### **8.4 Analysis Sets**

All subjects who receive any amount of study drug will be included in the evaluation of safety and efficacy, except for patients who take less than 80% of their prescribed dose of pembrolizumab and/or XL888 since they will be considered inevaluable for the primary endpoint of toxicity.

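### Evaluability for the toxicity endpoint is not tied to the DLT window, so DLT-free patients who stop later can be replaced and the DLT rate can be inflated

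*Combined protocol and SAP*

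**What the plan says.** Section 4.2.1 states that "The primary endpoint is still toxicity". That endpoint drives the 3+3 rule in Section 5.2.2, under which two or more DLTs in 3 or 6 patients reject a dose.

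The period over which DLTs count is short but given in two ways. Section 5.2.3 counts "treatment related adverse events during the first 21 days of therapy". Section 2.0 defines the MTD by the share of subjects who "experience a DLT in the first 4 weeks of treatment".

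Three passages decide who is evaluable, and none refers to that period:

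- Section 5.7.2: "Patients who do not complete the intended course of chemotherapy due to reasons other than toxicity will be considered as in-evaluable for the primary endpoint". These patients are replaced.
- Section 7.1.1.6: patients below 80% of prescribed pembrolizumab and/or XL888 "due to reasons other than toxicity will be considered inevaluable for the primary endpoint of toxicity and will be replaced".
- Section 8.4: all treated subjects are analysed "except for patients who take less than 80% of their prescribed dose of pembrolizumab and/or XL888 since they will be considered inevaluable". The limit to reasons other than toxicity, present in Section 7.1.1.6, is absent here.

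The intended course is not defined, and the regimen in Section 5.2 contains no chemotherapy. The only stopping reason in Section 5.7 worded as completing treatment is "Completed 24 months of uninterrupted treatment with pembrolizumab or 35 administrations of study medication, whichever is later". Confirmed progression is listed there as a separate reason to discontinue.

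**The concern.** In a 3+3 design, whether a patient had a DLT is known once the window closes. If evaluability depends on what happens afterwards, a valid observation can be discarded for reasons unrelated to toxicity in the window. Take a patient who completes the window without a DLT and stops for progression at the first scan. On the literal wording that patient has not completed the course, for a reason other than toxicity, and so becomes in-evaluable and is replaced. A patient who stops because of toxicity is kept.

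If DLT-free patients are discarded more often than DLT patients, each replacement is a fresh chance of a DLT, and a tolerable dose can look too toxic. The number of evaluable patients in a cohort also stays unsettled after the window has closed. With 3 to 6 patients per dose level, one or two reclassified patients can change the conclusion on a dose.

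**Working it through.** **Inputs from the plan.** The rejection rule is in Section 5.2.2. Section 8.1 gives 3 to 18 patients in escalation, 32 in expansion and 38 to 50 in total. Scan timing is in Section 7.1.4.4. Cycles last 21 days.

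**Assumed inputs.** The documents give none of these: p, the true DLT rate; q, the share of DLT-free patients removed and replaced; r, the share of DLT patients removed.

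**Step 1: the plan's own total.** Minimum: 2 levels × 3 + 32 = 38. Maximum: 3 levels × 6 + 32 = 50. Both agree with Section 8.1. The maximum is made up entirely of full cohorts, so it has no allowance for replacements.

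**Step 2: timing.** The first on-treatment scan falls on days 15 to 21 of cycle 3, which is study day 2 × 21 + 15 = 57 to 2 × 21 + 21 = 63. The DLT window closes on day 21 or day 28. Progression found at that scan therefore comes at least 57 − 28 = 29 days after DLT status is known.

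**Step 3: apparent DLT rate among evaluable patients.**

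a = p(1 − r) / [p(1 − r) + (1 − p)(1 − q)]

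With p = 0.20, r = 0, q = 0.25: a = 0.20 / (0.20 + 0.80 × 0.75) = 0.20 / 0.80 = 25.0%.

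**Step 4: chance that the 3+3 rejects the dose.** At a DLT probability x per evaluable patient:

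R(x) = [3x²(1 − x) + x³] + 3x(1 − x)²[1 − (1 − x)³]

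At x = 0.20: 0.104 + 0.384 × 0.488 = 0.291. The table uses R(a), which assumes that replacements are made before the escalation decision, and r = 0.

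| True rate p | q = 0: a, R | q = 10%: a, R | q = 25%: a, R | q = 50%: a, R |
|---|---|---|---|---|
| 10% | 10.0%, 9.4% | 11.0%, 11.1% | 12.9%, 14.5% | 18.2%, 25.2% |
| 20% | 20.0%, 29.1% | 21.7%, 32.9% | 25.0%, 40.0% | 33.3%, 57.2% |
| 30% | 30.0%, 50.6% | 32.3%, 55.1% | 36.4%, 62.8% | 46.2%, 78.1% |

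At p = 20%, patients enrolled per evaluable patient are 1 / [p + (1 − p)(1 − q)] = 1.09, 1.25 and 1.67 for q = 10%, 25% and 50%.

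**Step 5: let DLT patients be removed too.** With p = 20% and q = 50%:

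- r = 25%: 0.15 / (0.15 + 0.40) = 27.3%
- r = 50%: 0.10 / (0.10 + 0.40) = 20.0%, no bias
- r = 75%: 0.05 / (0.05 + 0.40) = 11.1%, understated

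The rate is inflated when q > r, unbiased when q = r, and understated when q < r.

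**Step 6: can DLT patients be removed under the text?** Yes, by two routes. Section 5.3.2 lets XL888 resume one level lower after some toxicities. A DLT patient who resumes and later stops for progression has also stopped for a reason other than toxicity. Separately, Section 5.2.3 makes inability to take more than 75% of XL888 because of toxicity a DLT. Intake at or below 75% is under the 80% cut-off of Section 8.4, which has no exemption for toxicity.

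**The case against.** The strongest defence is that the intended course was meant to be the DLT period. Replacing patients who leave before DLT assessment is complete is ordinary 3+3 practice, and the plan's other figures fit that reading better. Escalation is counted at 3 to 6 patients per level with no replacements, and Section 1.0 gives a 14-month trial with 6 months of average treatment. A 24-month course could not be completed within that time. It can also be argued that progression ends the course under Section 5.7, so a patient who progresses has completed it. The 80% threshold might likewise apply cycle by cycle, since Section 7.1.1.6 checks pill counts on day 1 of each cycle. These points bear on what was intended, but no passage states any of them. If the window was meant, the text should say so.

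A reader might go further and infer that the rule removes only DLT-free patients and therefore does inflate the DLT rate. The documents do not support this. No passage says that DLT patients always stay evaluable, and Step 6 shows two ways in which they can be lost. There is some reason to expect q > r: stopping for toxicity is exempt from replacement, and Sections 5.3.1 and 5.3.2 end treatment for several severe toxicities. That makes inflation plausible but does not establish it.

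A reader might also infer that escalation decisions would be reopened months later. Sections 5.2.2 and 10.5 require committee approval before escalation but do not say how a later removal is handled. If decisions are taken when the window closes, progression around week 9 affects the final tally and the replacements rather than the decision itself.

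**Conclusion.** The point stands as a defect in the wording with a conditional effect. Sections 5.7.2 and 7.1.1.6 do not tie evaluability for the toxicity endpoint to the DLT window. Followed as written, they can replace a patient whose DLT-free result is already complete, and the denominator can change after the window has closed.

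The direction and size of any bias cannot be fixed from the documents. Inflation requires DLT-free patients to be removed more often than DLT patients. At a true rate of 20% with no DLT patient removed, the effect runs from slight (10% replaced: 21.7% apparent) to large (50% replaced: 33.3% apparent). The corresponding rise in rejection chance, from 29.1% to between 32.9% and 57.2%, also requires replacement before the escalation decision. Equal removal gives no bias, and heavier removal of DLT patients understates toxicity. The case for change is that the denominator of the primary endpoint should not depend on which of these happens.

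**What to change.** - In Sections 5.7.2 and 7.1.1.6, define a DLT-evaluable patient as one who had a DLT, or who completed the DLT window with the required share of the doses due in it.
- Replace only patients lost or under-dosed within the window for reasons other than toxicity.
- State that progression, withdrawal or missed doses after the window do not change evaluability and do not trigger replacement.
- Align Section 8.4 with this, so that a patient with a DLT is always counted.
- Reconcile the 21-day window in Section 5.2.3 with the 4-week window in Section 2.0, so that evaluability refers to one stated period.

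The cost is a wording amendment to these sections. It needs no extra patients or procedures and, compared with the literal reading, should reduce replacements.
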